7. PLANNED ANALYSIS

For End-Of-Text (EoT) tables, the set of summary statistics is: N / Mean / SD / Min / Median / Max.

For tables that are provided for endpoints with some extreme data, median, quartiles and percentiles should be preferred to mean, standard deviation, minimum and maximum

Tabulations of frequencies for categorical data will include all possible categories and will display the number of observations in a category as well as the percentage (%) relative to the respective treatment group (unless otherwise specified, all patients in the respective patient set whether they have non-missing values or not). Percentages will be rounded to 2 decimal places. The category missing will be displayed only if there are actually missing values.

7.1 DEMOGRAPHIC AND OTHER BASELINE CHARACTERISTICS

Only descriptive statistics are planned for this section of the report.

7.2 CONCOMITANT DISEASES AND MEDICATION

Concomitant diseases will be coded by the latest version of Medical Dictionary for Regulatory Activities (MedDRA). Only descriptive statistics are planned for concomitant diseases.

Concomitant medication will be coded by latest version of “Nihon-iyakuhinshu”.

7.3 TREATMENT COMPLIANCE

It is not planned to analyse treatment compliance.

7.4 PRIMARY ENDPOINT(S)

There is no primary endpoint for efficacy as the primary objective of the PMS study is the evaluation of safety.

7.4.1 Primary analysis of the primary endpoint(s)

The analysis will be performed as defined in the NIS Protocol (see the NIS Protocol Section 7.3.1).

7.4.2 Sensitivity analysis, subgroup analysis, exploratory analysis of the primary endpoint(s)

The subgroup analysis will be performed (see [Section 6.4](#)).

7.5 SECONDARY ENDPOINT(S)

7.5.1 Key secondary endpoint(s)

7.5.1.1 Primary analysis of the key secondary endpoint(s)

[figure not shown]
This section is not applicable as no key secondary endpoint has been specified in the NIS protocol.

7.5.1.2 Sensitivity analysis, subgroup analysis, exploratory analysis of the key secondary endpoint(s)

This section is not applicable as no key secondary endpoint has been specified in the NIS protocol.

7.5.2 (Other) Secondary endpoint(s)

For the change from baseline in HbA1c and FPG at the last observation, descriptive statistics will be calculated based on the efficacy set. A 95% confidence interval for the mean change from baseline will also be calculated.

7.7 EXTENT OF EXPOSURE

Only descriptive statistics are planned for this section of the report.

7.8 SAFETY ANALYSIS

All safety analyses will be performed on the safety set.

7.8.1 Adverse events

Unless otherwise specified, the analyses of adverse events (AEs) will be descriptive in nature. All analyses of AEs will be based on the number of patients with AEs and NOT on the number of AEs.

Furthermore, for analysis of AE attributes such as duration, severity, etc. multiple AE occurrence data on the CRF, will be collapsed into AE episodes provided that all of the following applies:

- The same MedDRA lowest level term was reported for the occurrences
- The occurrences were time-overlapping or time-adjacent (time-adjacency of 2 occurrences is given if the second occurrence started on the same day or on the day after the end of the first occurrence)
- Treatment did not change between the onset of the occurrences OR treatment changed between the onset of the occurrences, but no deterioration was observed for the later occurrence

For further details on summarization of AE data, please refer to BI standards ('Analysis and Presentation of Adverse Event Data from Clinical Trials' [\(2\)](#)).

An overall summary of adverse events will be presented.

The frequency of patients with the following items will be summarized by primary SOC and PT.

- AEs
- ADRs
- serious AEs
- serious ADRs
- AEs leading to death
- ADRs leading to death
- AEs leading to discontinuation
- ADRs leading to discontinuation

AEs will also be reported by intensity. The frequency of patients with ADRs occurred in summer (the onset date is in June, July, August, or September) will also be summarized.

In addition, summaries for the time to onset of first episode for the ADRs will be tabulated, by duration (<2weeks, 2 to <4 weeks, 4 to <6 weeks, 6 to <8 weeks, 8 to <10 weeks, 10 to <12 weeks, 12 to <36 weeks, 36 to <60 weeks, 60 weeks to <72weeks, 72 weeks to 84 weeks

to <96weeks, 96 weeks to <108weeks, 108 weeks to <120weeks, 120 weeks to <132weeks, 132 weeks to <144weeks, 144 weeks to <156weeks, ≥156 weeks), by primary SOC, and PT.

The SOCs will be sorted according to the standard sort order specified by European medicines agency, PTs will be sorted by frequency (within SOC).

An ADR is defined as an AE for which either the investigator or the sponsor (or both) assess the causal relationship to JARDIANCE[®] either as “Possibility high”, “Possibility low”, or “Unknown”.

A serious AE is defined as an AE for which either the investigator or the sponsor (or both) assess the seriousness as “Serious”.

AE analyses will be carried out after integrating AE data from CRF and AE data from Local PV safety database (Perceive).

[figure not shown]
In addition, events coded as “no adverse event”, etc. will not be included in the AE analyses. The list of codes will be provided by Drug Safety.

[figure not shown]
Priority survey items, Important identified risk, Important potential risks and Significant ADRs

The following AEs are summarised on the basis of the Standardised MedDRA queries (SMQs) or Boehringer Ingelheim customised MedDRA query (BICMQ) by primary SOC and PT.

*:1 ADRs are also summarised.

*2: ADRs occurred in summer (the onset date is in June, July, August, or September) are also summarized.

Risk ratios with 95% confidence intervals will be shown for subgroup analyses. In case that there will be the significant difference between each factor, the frequency of patients with drug related AEs (ADRs) and with serious AEs will be summarized by primary SOC and PT. Due to the high number of exploratory subgroup analyses, it is recognised that the likelihood of chance findings is high and therefore subgroup results should be interpreted with caution.

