### 7.2 NULL AND ALTERNATIVE HYPOTHESES

The analyses in this PMS are descriptive and exploratory by nature. No formal hypotheses tests will be made.

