### **7.3.3 Safety analyses**

The analysis and reporting of adverse events will concentrate on treatment-emergent adverse events. To this end, all adverse events occurring between first drug intakes until 7 days after last treatment administration will be considered ‘treatment-emergent’. Adverse events that start before first drug intake and deteriorate under treatment will also be considered as ‘treatment-emergent’.

AEs will be coded using lowest level terms of the Medical Dictionary for Drug Regulatory Activities (MedDRA). AEs occurring in routine medical practice will be evaluated. The relationship of an AE to JARDIANCE® Tablets will be assessed by the investigator and the sponsor. An ADR is defined as an AE if either the investigator or the sponsor (or both) assess the causal relationship of JARDIANCE® Tablets either as “Possibility high”, “Possibility low” or “Unknown”.

The frequency of ADRs will be tabulated by system organ class and preferred term according to the current MedDRA version. The frequency of SAE will also be tabulated likewise.

The incidence of ADRs stratified based on patient demographics will also be investigated.

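### SAP 7.8.1 makes by-reaction subgroup tables of ADRs and serious AEs depend on a significant difference; the elderly, renal and hepatic groups targeted at the authority's request should be exempt

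*SAP*

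**What the plan says.** SAP 7.8.1 first promises, without condition, that "Risk ratios with 95% confidence intervals will be shown for subgroup analyses". The next sentence adds a second level of detail under a condition: "In case that there will be the significant difference between each factor, the frequency of patients with drug related AEs (ADRs) and with serious AEs" are summarised by SOC and PT. The section then cautions that "it is recognised that the likelihood of chance findings is high".

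Other safety output carries no such condition. SAP 7.8.1 tabulates AEs, ADRs and serious AEs by SOC and PT for the whole safety set. It also gives summaries of priority risks: "The following AEs are summarised on the basis of the Standardised MedDRA queries (SMQs" or the sponsor's own queries.

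On the purpose of the analyses, Protocol 7.2 says "The analyses in this PMS are descriptive and exploratory by nature" and rules out formal hypothesis tests. Protocol 7.3.3 adds, with no significance condition, "The incidence of ADRs stratified based on patient demographics will also be investigated". SAP 7.8.1 opens with "Unless otherwise specified, the analyses of adverse events (AEs) will be descriptive in nature".

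On subgroups, SAP 7.4.2 says under the primary endpoint that "The subgroup analysis will be performed" and refers to SAP 6.4, which is redacted. Protocol 7.3.1 defines the primary endpoint as the number of patients with ADRs. Protocol 7.6 says that elderly patients and those with renal or hepatic dysfunction are targeted at the request of the Japanese authority. Protocol 3.3 expects 100 of each.

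**The concern.** A non-significant risk ratio in a group of about 100 patients does not show that its reaction profile matches that of everyone else. Showing the by-reaction table only after a significant result treats it as if it did.

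The effect depends on what is screened. If it is the overall ADR risk ratio, which the placement of subgroup analysis in SAP 7.4.2 suggests, an increase confined to one reaction is diluted among all other ADRs. The table that would reveal it is then often not made. If the screen works reaction by reaction, the subgroup counts by reaction must already exist before it can be applied, so the condition saves little work.

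The SAP's own caution about chance findings points the same way. Where significance is acknowledged to be unreliable, it is a weak basis for choosing which safety detail to show. This matters most for the three patient groups that the protocol set out to include.

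**Working it through.** **The plan's own figure.** Protocol 7.6 says that 3,000 completers give a 95% (99%) chance of at least one case of an ADR with true incidence 0.10% (0.16%). By 1 − (1 − p)^3000, p = 0.0010 gives 95.03% and p = 0.0016 gives 99.18%. Both reproduce. They concern the whole set, not a subgroup.

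**Inputs from the documents.**
- Target of 100 per group (Protocol 3.3).
- 14.6% elderly: 0.146 × 3,000 = 438. 14.8% renal: 0.148 × 3,000 = 444. 13.7% hepatic: 0.137 × 3,000 = 411 (Protocol 7.6).
- The hepatic group is moderate or severe only (Protocol 3.3), whereas the 13.7% is for hepatic function disorder without that limit. The hepatic group may therefore be much smaller than 411.

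**Assumptions.** The documents give no ADR rate.
- Significant means that the 95% CI of the risk ratio excludes 1.
- The subgroup (n) is compared with all remaining patients (N − n).
- One reaction has incidence 1% elsewhere and 3% in the subgroup.
- The overall ADR rate is 10% elsewhere (range 5–20%) and 2 points higher in the subgroup. This places every extra reaction in a patient with no other ADR, which favours the screen.

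**Method.** For counts x1 of n1 and x2 of n2, SE(log RR) = √(1/x1 − 1/n1 + 1/x2 − 1/n2). The screen opens if |log RR| > 1.96 × SE. Its probability is the sum of the binomial probabilities over all (x1, x2) that open it.

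**Illustration at the expected counts, n = 438 against 2,562.**
- Overall ADRs: 52.6 v 256.2 patients, RR 1.2, log RR 0.182, SE 0.142, CI about 0.91 to 1.59. It includes 1, so no table.
- The single reaction: 13.1 v 25.6 patients, RR 3, log RR 1.099, SE 0.335, CI about 1.55 to 5.79. It excludes 1.

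**Probability that the screen opens.**

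| Subgroup n of N | Overall ADRs 10%→12% | 5%→7% | 20%→22% | Per reaction 1%→3% |
|---|---|---|---|---|
| 30 of 3,000 | 0.084 | | | 0.227 |
| 50 of 3,000 | 0.098 | | | 0.301 |
| 100 of 3,000 | 0.126 | 0.181 | 0.097 | 0.426 |
| 438 of 3,000 | 0.261 | 0.410 | 0.174 | 0.847 |
| 548 of 3,750 | 0.309 | 0.483 | 0.202 | 0.910 |
| 730 of 5,000 | 0.384 | 0.595 | 0.249 | 0.965 |
| 876 of 6,000 | 0.441 | 0.666 | 0.286 | 0.984 |

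The last three rows allow for a safety set larger than the completer target: 3,000 divided by assumed completion of 80%, 60% and 50%, with 14.6% in the subgroup. The rows with n = 30 and 50 are assumed sizes for a small hepatic group.

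**Broad rise.** If overall ADRs go from 10% to 15%, the overall screen opens 39% of the time at n = 100 and 85% at n = 438.

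**What an unconditional table would show at n = 438.** 0.03 × 438 = 13.1 patients with the reaction, against 0.01 × 438 = 4.4 expected at the background rate.

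**The case against.** The strongest reply is that the decisive text is not visible. SAP 7.4.2 sends the reader to 6.4 for subgroups, and that section is redacted, as is part of 7.8.1. A reader might infer that the plan never defines the outcome or threshold behind the significant difference. The documents do not support that: redacted text is not missing text, and 6.4 may define the trigger or already exempt these groups. This part of the objection stands, so the point here is the stated condition itself and the fix is worded accordingly.

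A reader might also infer that the screen contradicts the protocol. It does not. The statement that AE analyses are descriptive allows for exceptions, Protocol 7.3.3 promises stratified incidence rather than by-reaction subgroup tables, and the unconditional risk ratios address that promise. The screen is a poor fit with a plan that makes no tests, no more.

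Nor does anything readable say that the authority asked for by-reaction tables; it asked that these patients be included. That they deserve this detail is a statistical judgement, not a documented requirement.

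Finally, the size depends on assumed rates, and n = 100 is the low end for elderly and renal patients, of whom Protocol 7.6 expects 400 to 500. That also stands. With a per-reaction screen at those sizes, the loss is small.

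**Conclusion.** The concern holds in a limited form. As readable, SAP 7.8.1 lets a significance screen decide whether by-reaction ADR and serious AE tables appear for the groups that the protocol targets at the authority's request.

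Under the stated assumptions, a threefold rise in one reaction opens an overall-ADR screen about 13% of the time at n=100 (10–18% over background rates of 5–20%) and 26% at n=438 of 3,000 (17–41%). A per-reaction screen opens 43% and 85% of the time. For a hepatic group of 30 to 100, the figures are 8–13% and 23–43%. The loss is therefore material if the screen is the overall ratio or the subgroup is small, and minor if it works per reaction at the expected elderly and renal sizes.

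The point does not touch the primary analysis, and subgroup safety results as such are not withheld. Everything rests on the visible text, since 6.4 could already resolve it.

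**What to change.** Check SAP 6.4 first. Unless it already does so, add to SAP 7.8.1 that SOC/PT tables of ADRs and of serious AEs are produced regardless of the risk ratio:

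- by age: ≥75 v <75 years;
- by renal function: eGFR 45 to <60 in its own column, beside ≥60 and <45;
- by hepatic dysfunction grade: moderate/severe v normal/mild.

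The renal columns should not be pooled. There are no exclusion criteria (Protocol 3.3.3) and the grades in Protocol 3.3 extend below 30, so comparing eGFR 45 to <60 with all other patients would mix worse renal function with normal function and could hide a gradient.

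Leave the conditional tables for other factors as they are. The cost is a short SAP addition and three sets of tables from programs that are needed anyway; the downside is slightly longer output.

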7.8.2 Laboratory data

Mean \pm SD table and figure by visit of hematocrit, hemoglobin, total cholesterol, LDL cholesterol, HDL cholesterol, triglyceride and eGFR. To calculate eGFR, see the NIS Protocol Section 5.3.3. Change from baseline of weight by visit will be also displayed.

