## **2. RATIONALE, OBJECTIVES, AND BENEFIT-RISK ASSESSMENT**

### **2.1 RATIONALE FOR PERFORMING THE STUDY**

In Japan, post-approval execution of post marketing surveillance (PMS) is requested by the Japanese Pharmaceutical Affairs Law (J-PAL) in order to accumulate safety and efficacy data for re-examination. Re-examination period is defined by J-PAL. New integrant is 8 years for re-examination. Eight years after approval of a new substance, results of PMS need to be submitted as a part of re-examination dossier to the Japanese regulatory authority, the Ministry of Health, Labour and Welfare (MHLW).

Collected data from PMS will be included in the Japanese periodic safety reports and submitted to MHLW on designated dates until the end of re-examination period.

The protocol may be revised because of new information or knowledge obtained in the course of conducting PMS. When a change of the approved label such as in dosage and administration or indications is made during the re-examination period of JARDIANCE® Tablets (except that for this change a re-examination period is newly designated by MHLW) and NBI finds it necessary to revise this protocol, handling each matter should be discussed and the protocol may be revised. If any issue or concern arises (e.g. suggestion of a potential for clinically significant adverse reaction, remarkable increase in incidence of an adverse reaction, or any issue or concern on safety or efficacy assessment made prior to the approval of JARDIANCE® Tablets) in the course of PMS, implementation of additional special surveillance or post-marketing clinical trial should be discussed to identify or confirm a cause or estimated cause of such issue. Special surveillance is defined by J-PAL. It means surveillance for long-term use or special patient population (elderly, renal/hepatic dysfunction etc.).

SGLT-2 inhibitor is a drug class with a new mode of action, and does not comprise sufficient Japanese safety data within the class. It's not that there is a particular safety issue concerning JARDIANCE®; however, further surveillance is needed to monitor possible increase in the incidence of malignant tumor which is potentially associated with drugs of the same class, as well as the effect on kidneys attributable to its mode of action by which a long-term use stimulates the urinary excretion of glucose, and also the effect on hepatic function and bone metabolism.

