#### **5.3.3 Assessment of safety laboratory parameters**

The laboratory tests will be performed when required by investigator.

Safety laboratory assessment will be performed according to local practice and if available the following parameters will be recorded in the eCRFs:

Haematology	Erythrocyte count (RBC), haemoglobin (Hb), haematocrit (Hct), Leukocyte counts (WBC) and platelet count.
Blood chemistry	HbA1c , Fasting plasma glucose, sodium (Na), potassium (K), chlorine (Cl), magnesium (Mg), calcium (Ca), phosphorus (P), creatinine (CRE), aspartate transaminase (AST, SGOT), alanine transaminase (ALT, SGPT), alkaline phosphatase (ALP), gamma-glutamyl-transferase ( $\gamma$ -GTP), albumin , lactic dehydrogenase (LDH), total bilirubin (T-BIL), blood urea nitrogen (BUN), total cholesterol (T-CHO), HDL cholesterol (HDL), LDL cholesterol (LDL), Triglycerides (TG), Amylase (AMY), Lipase (LIP) , uric acid (UA), 25-OH vitamin D, iPTH, ketone and creatine kinase (CK).
Urinalysis	Glucose, protein, urobilinogen, sediment, albumin, ketone and creatinine.

Enzymatic method:

$$\text{eGFR (mL/min/1.73 m}^2) = 194 \times \text{Creatinine (mg/dL)}^{-1.094} \times \text{Age}^{-0.287}$$

For female,  $\times 0.739$

Jaffe rate assay:

$$\text{eGFR (mL/min/1.73 m}^2) = 175 \times \text{Creatinine (mg/dL)}^{-1.154} \times \text{Age}^{-0.203}$$

For female,  $\times 0.742$

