7.8.3 Vital signs

Change from baseline of blood pressure (SBP and DBP) and pulse by visit.

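### The visible SAP 7.8.2 summarises eGFR and the other listed laboratory tests by visit mean and SD without within-patient change, so a fall in eGFR could be masked if patients with lower eGFR leave or are tested less

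*SAP*

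**What the plan says.** SAP 7.8.2 gives a table and figure of mean and SD by visit for seven parameters: "hematocrit, hemoglobin, total cholesterol, LDL cholesterol, HDL cholesterol, triglyceride and eGFR". The only change from baseline in that section is for body weight: "Change from baseline of weight by visit will be also displayed". SAP 7.8.3 plans "Change from baseline of blood pressure (SBP and DBP) and pulse by visit".

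Protocol 2.1 gives the reasons for the surveillance. One is "the effect on kidneys attributable to its mode of action by which a long-term use stimulates the urinary excretion of glucose", followed by "and also the effect on hepatic function and bone metabolism".

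Four other provisions decide which laboratory values reach the tables:

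- Protocol 5.3.3 leaves laboratory testing to the investigator and records results if they are available.
- SAP 6.1 counts laboratory values as on treatment up to 3 days after the last intake.
- SAP 6.6 plans no imputation in the efficacy or safety analyses, apart from AE and partial dates.
- Protocol 7.4 uses the repeated-measures model for missing data in continuous efficacy endpoints, which does not extend to laboratory safety data.

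**The concern.** A reader will judge the course of eGFR by comparing the Week 156 mean with the baseline mean. The first comes from patients still on treatment and still tested after three years, and the second from everyone with a baseline value. The difference mixes true change within patients with a change in who contributes. If patients with lower baseline eGFR stop earlier or are tested less, the later means rise for that reason alone, and a real decline can look flat or even like a gain.

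The study has no control group (Protocol 3.2), so within-patient change is the most direct laboratory evidence available on an effect that Protocol 2.1 names. The SAP already uses it for weight and vital signs, but not for eGFR.

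**Working it through.** **The plan's own figure.** The only statistical figure in Protocol 7.6 is the chance of seeing at least one ADR among 3,000 completers, 1 − (1 − p)^3000. For p = 0.10% this is 95.03%, and for p = 0.16% it is 99.18%. Both reproduce the stated 95% and 99%. They say nothing about eGFR, for which the plan gives no SD, slope or precision. Nor does it give a dropout rate: it sets no enrolment target, so none can be derived. Everything below is an assumption chosen to show scale.

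**Step 1: drift of the raw mean with no true change.** Assume baseline eGFR is normal with SD 20 (the mean, say 75, does not affect the result). Let the odds of still contributing at Week 156 be multiplied by OR per 10 mL/min/1.73m². The log-odds per SD are then k = 2 × ln(OR), which is 0.191, 0.365 and 0.525 for OR 1.1, 1.2 and 1.3. With P(x) the logistic probability of remaining, and its intercept set to give the chosen retention, drift = E[x·P(x)] / E[P(x)] − E[x].

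| Retention | OR 1.1 | OR 1.2 | OR 1.3 |
|---|---|---|---|
| 50% | +1.9 | +3.5 | +4.9 |
| 70% | +1.1 | +2.1 | +3.0 |
| 80% | +0.8 | +1.4 | +2.0 |

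A hand check for small k is drift ≈ SD × k × (1 − retention). For OR 1.1 at 50% this gives 20 × 0.191 × 0.5 = 1.9. At OR 1 the drift is zero.

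**Step 2: what paired change recovers.** A simulation of 1,000,000 patients per scenario assumed baseline mean 80, SD 20, a slope of −1 per year (SD 2) and measurement SD 6. The true three-year change is therefore −3.0. Retention depended on underlying baseline eGFR with log-odds of 0.3 or 0.5 per SD, which is an OR of about 1.16 or 1.28 per 10 units. In the last two rows it also depended on slope (0.3 per SD).

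| Summary | 80% kept | 70% | 60% | 50% |
|---|---|---|---|---|
| Raw difference, retention unrelated to eGFR | −3.0 | −3.0 | −3.0 | −3.0 |
| Raw difference, 0.3 on baseline | −1.8 | −1.2 | −0.6 | −0.1 |
| Raw difference, 0.5 on baseline | −1.1 | −0.1 | +0.8 | +1.7 |
| Paired change, either baseline case | −3.0 | −3.0 | −3.0 | −3.0 |
| Raw difference, 0.5 on baseline and 0.3 on slope | −0.8 | +0.3 | +1.4 | +2.5 |
| Paired change, same case | −2.7 | −2.5 | −2.3 | −2.2 |

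Paired change removes the distortion due to selection on baseline eGFR. It reduces, but does not remove, the distortion when patients who decline faster also leave.

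**The case against.** The strongest reply is that this is a descriptive surveillance study with no hypothesis tests (Protocol 7.2), that the bias is assumed, and that kidney effects have another route into the report. Much of this stands, and it rules out four stronger readings.

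- **A reader might infer that the plan cannot show renal, hepatic or bone effects.** The documents do not support that. Protocol 5.2.2.1 allows an abnormal laboratory finding to be an AE. SAP 7.8.1 tabulates AEs and ADRs by system organ class and preferred term and adds summaries based on MedDRA queries, so overt events can appear there. The route is incomplete, however. Protocol 5.3.1 makes collection mandatory for ADRs and fatal AEs, although the visit tables in 6.2.2 and 6.2.3 ask for any new AE. A gradual fall in eGFR that nobody reports as an event would not reach those tables.
- **A reader might infer that visit means are the only laboratory analysis, and that liver and bone tests go unanalysed.** Neither can be confirmed. The SAP contents list shows a redacted entry between section 5.2.2 (page 8) and section 6 (page 16), and others where 6.4 and 7.6 would fall. The list of risk topics in 7.8.1 is not visible either. Further laboratory output may be in that text.
- **A reader might infer that eGFR will be biased.** No dropout rate or pattern is given, and the raw means are unbiased if missingness is unrelated to eGFR.
- **A reader might claim a large loss of precision from √(1/(1 − r)), which is 2.2 at a within-patient correlation r of 0.8.** That formula needs equal numbers at both visits and no overlap between the two means. With N patients at baseline and a random half retained, those patients are in both means. The variance of the raw difference is (3 − 2r)SD²/N, against 4(1 − r)SD²/N for paired change. The ratio of standard errors is √((3 − 2r)/(4(1 − r))) = 1.15, 1.32 and 1.73 for r = 0.7, 0.8 and 0.9. The plan attaches no interval or test to this contrast in any case, so precision is not the argument.

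The descriptive aim does not answer the remaining point, because paired change is itself descriptive.

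**Conclusion.** The point holds for the visible text. SAP 7.8.2 gives eGFR, hematocrit, hemoglobin and the lipids by visit mean and SD with no within-patient change, while the SAP plans change from baseline for weight, blood pressure and pulse. Discretionary testing, the on-treatment limit and the lack of a missing-data method for laboratory data mean that visit means can compare different patients.

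The size is conditional. Under the assumed selection (SD 20, OR 1.1 to 1.3 per 10 mL/min/1.73m²), the raw mean drifts up by about 1.9 to 4.9 at 50% retention and by 0.8 to 2.0 at 80%. Drift of that size could hide part or all of a true 3-point fall, or reverse it. Without selection on eGFR the drift is nil. This is a risk that the plan leaves open, not a demonstrated bias. The liver and bone parameters are a query that depends on what the redacted text contains.

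**What to change.** In SAP 7.8.2, keep the raw means and add at each visit, for eGFR and the other six listed parameters, the mean change from baseline with a 95% confidence interval and the number of patients who have both values. State also which visit windows apply, because SAP 6.7 ties Table 6.7: 1 to the efficacy analyses.

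For liver and bone, confirm that the redacted sections already summarise the collected parameters and cite the place. If they do not, summarise AST, ALT, ALP, total bilirubin, calcium, phosphorus and, where available, 25-OH vitamin D and iPTH in the same way. The last two may rest on few, selected patients, so the counts matter.

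The cost is a few extra columns and perhaps a few more parameters, all from data that Protocol 5.3.3 already places in the eCRF. The report should say that paired change removes selection on baseline eGFR but not all selection on slope or on discretionary testing, and that without a control group it does not separate a drug effect from natural decline.
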